7.4 Definitions

7.4.1 Definitions of Adverse Events

The following definitions have been adapted from the 2010 FDA reporting regulations and International Conference on Harmonisation (ICH) guidelines for use in this study:

- i. Adverse Event (AE): An adverse event (AE) is defined as any reaction, side effect, or untoward medical event that occurs during the course of the clinical trial associated with the use of a drug in humans, whether or not the event is considered related to the treatment or clinically significant. For this study, AEs will include events reported by the patient, as well as clinically significant abnormal findings on physical examination or laboratory evaluation. A new illness, symptom, sign or clinically significant laboratory abnormality or worsening of a pre-existing condition or abnormality is considered an AE.

- ii. Suspected Adverse Reaction: Suspected adverse reaction means any adverse event for which there is a *reasonable possibility* that the drug caused the adverse event. For the purposes of IND safety reporting, ‘reasonable possibility’ means there is evidence to suggest a causal relationship between the drug and the adverse event. A suspected adverse reaction implies a lesser degree of certainty about causality than adverse reaction, which means any adverse event caused by a drug. For this study, a suspected adverse reaction will be any event reported by the patient, as well as clinically significant abnormal findings on physical examination or laboratory evaluation that are thought to be related to the MRI exam or liver biopsy.

- iii. Expected adverse event: Several complications are expected to happen in subjects with hematologic conditions (such as hemolytic anemia, painful crisis, etc.) MIDAS expected adverse events are listed in Table 3 and 4.

- v. Unexpected adverse event or unexpected suspected adverse reaction: A MIDAS unexpected AE or unexpected suspected adverse reaction is any AE or SAR that is not a MIDAS expected AE or SAR (listed in Table 3) or not listed at the specificity or severity that has been observed.

Table 3. List of MIDAS expected and potentially serious adverse events in all subjects.

Hematologic Disease Symptoms and Associated Conditions		
Abnormal TCD velocities	Hand-foot syndrome/dactylitis	
Acute chest syndrome	Hematuria	Pain, sternal or rib
Albuminuria	Hemiplegia	Priapism
Amenorrhea	Hemolysis	Proteinuria
Anemia (severe)	Hemorrhagic Stroke	
Aplastic crisis	Hepatic sequestration	Pneumonia
Arthralgia	Hepatomegaly	Pulmonary embolism
Avascular necrosis of hip/shoulder		Pulmonary hypertension
Bacteremia	Hyperbilirubinemia	Pulmonary infiltrate on chest x-ray
Bone infarction	Hypersplenism	Pyelonephritis
Cardiac arrhythmia	Hypertension	Renal failure
Cardiomegaly	Hypocalcemia	Renal insufficiency
Cerebrovascular accident	Hyposthenuria	Renal papillary necrosis
Cholecystitis	Hypotension	Reticulocytopenia
Cholelithiasis	Hypoxemia (PO ₂ < 65mm Hg)	Reticulocytosis (10%–20%)
Cognitive dysfunction	Ileus	Retinopathy
Constipation	Infection, other bacterial	Retinal hemorrhage
Cranial nerve palsy	Infection, pneumococcal	Rhabdomyolysis
Death	Infection, line	Seizure
Decreased renal function	Infection, viral	Septicemia
Decreased lung function	Jaundice	Silent infarct
Delayed growth/puberty	Leukocytosis	Skin ulcer
Depression	Meningitis	Splenic sequestration
Dizziness	Nephropathy	Splenomegaly
Electrolyte imbalance	Osteomyelitis	TCD velocity, transient increase or decrease, or TCD alert
Elevated urinary urobilinogen	Pain, back	TIA
Elevated serum transaminases	Pain, chest	Transfusion, unanticipated
Elevated TCD velocities	Pain, joint	Vaso-occlusive pain
Fever	Pain, long bone	

7.4.2 Adverse Event/Suspected Adverse Reaction Severity Grades

MIDAS uses the Common Terminology Criteria for Adverse Events (CTCAE), version 4.0, for detailed descriptions of Severity Grades. The CTCAE is classified by body system and AE and provides descriptions of events that qualify under each severity rating.

Grade refers to the severity of the AE. The CTCAE displays Grades 1 through 5 with unique clinical descriptions of severity for each AE based on this general guideline:

Grade 1 Mild; asymptomatic or mild symptoms; clinical or diagnostic observations only; intervention not indicated.

Grade 2 Moderate; minimal, local or noninvasive intervention indicated; limiting age-appropriate daily activities and tasks.

Grade 3 Severe or medically significant but not immediately life-threatening; hospitalization or prolongation of hospitalization indicated; disabling; limiting self care activity of daily living (ADL)**.

Grade 4 Life-threatening consequences; urgent intervention indicated.

Grade 5 Death related to AE.

**Self care ADL refer to bathing, dressing and undressing, feeding self, using the toilet, taking medications, and not bedridden.

Grade 1 AE/SARs are not entered in the electronic CRF or captured in the MIDAS database.

7.4.4 *Adverse Event Outcome*

The terms used to describe AE outcome are as follows:

Ongoing

Resolved without sequelae

Resolved with sequelae

8.0 DATA COLLECTION AND CONFIDENTIALITY

8.1 Data Collection

Data collection and data management for this investigation will be conducted through the SJCRH Hematology Department. Co-investigators and CRAs assigned to this protocol will be responsible for assisting the PI in assuring protocol compliance as well as reviewing, transcribing and tracking of all clinical and safety related data.

Clinical data will be transcribed from source documents to the study database. This ensures that all protocol required data elements are captured. A database will be created for this study by the Clinical Research Informatics Division. Data will be entered by a Clinical Research Associate (CRA).

8.2 Study Monitoring

The Principal Investigator and study team are responsible for ensuring protocol compliance. The study team will hold quarterly team meetings and review case histories or quality summaries on participants.

Source document verification of eligibility and the informed consent process for 100% of St. Jude participants will be performed by The Eligibility Coordinators.

The Clinical Research Monitors will review up to 10% of the study participants annually for appropriateness of the informed consent process, eligibility, SAE reporting (TRACKS), and patient status. Additional information may be monitored at the request of the IMC, the IRB, or other institutional administration. The Monitor will generate a formal report which is shared with the Principal Investigator (PI), study team and the Internal Monitoring Committee (IMC).

Continuing reviews by the IRB and CT-SRC will occur at least annually. In addition, SAE reports in TRACKS (Total Research and Knowledge System) are reviewed in a timely manner by the IRB/ OHSP.

8.3 Confidentiality

Records from the study which identify the study participant will be kept confidential in a password-protected database. Access to study database will be allowed only to study investigators and designated CRAs. Subject identifiers will be removed from any published material.

9.0 STATISTICAL CONSIDERATIONS

This is a non-therapeutic, prospective study aimed to develop a novel R2*-UTE imaging sequence technique to non-invasively and accurately estimate high hepatic iron content (HIC) values (≥ 25 mg Fe/g). The current standard management procedure for patients at risk of iron overload at St. Jude is to estimate their (HIC) by the calibrated R2*-GRE imaging technique, which becomes unreliable when HIC is greater than 25 mg Fe/g. Therefore, the success of the study will provide better monitoring and guidance to the clinical management of patients with massive iron overload.

The primary objective is to test the association of hepatic iron content (HIC) measured with the newly developed 1.5T R2*-UTE technique and HIC quantified by liver biopsy in subjects with iron overload. The liver biopsies will be obtained as indicated by good clinical management practice, and it is expected that most research participants who will receive the liver biopsy will have an inconclusive result by the R2*-GRE method. The iron quantification assessed in liver biopsies will be correlated with the R2*-UTE signals. If the correlation is sufficiently high, then a statistical model relating HIC by R2*-UTE and liver biopsy values will be established, as was done for R2*-GRE.³²

9.1 Power and Accrual

Based on MRIRON study, we found that the correlation between R2*-GRE and HIC is 0.56 for patients with HIC > 15 mg Fe/g. The new R2*-UTE technique is expected to perform better for measuring high HIC values. Therefore, instead of testing if the r_{UTE} is different from zero, here we wish to test if the r_{UTE} is greater than 0.6. The one-sided testing hypotheses can be formulated as below: the null hypothesis $H_0: r_{UTE} \leq 0.6$ against the alternative hypothesis $H_a: r_{UTE} > 0.6$ we assume the true r_{UTE} to be 0.8. The study will be designed to have a significance level at $\alpha = 0.05$ and power at $1 - \beta = 0.8$. Although the parameter space for H_0 is large, to estimate the required sample size, we only need to consider the scenario that requires the largest sample size, which is: $H_0: r_{UTE} = 0.6$ v.s. $r_{UTE} = 0.8$. Based on a one-sided test, this design requires **41** liver biopsy samples.

We hope to accrue about 10-12 liver biopsies per year, so it will take approximately 4 years to achieve the desired sample size. Study subjects will be allowed to participate on the study only once in order to avoid potential bias introduced by repeat measurements on the same patient. There is a small chance that the liver biopsy specimen may be deemed inadequate due to technical sampling reasons. In this case, we will amend the protocol and continue patient accrual until we have obtained 41 evaluable liver biopsy specimens.

Approximately 20% of patients with iron overload have HIC values above 25 mg Fe/g, placing them in the category of massive iron overload. Because we aim at obtaining 41 liver biopsies for the analysis of the primary objective, we estimate that approximately 200 patients will undergo MRI testing with both R2*-GRE and R2*-UTE.

Healthy volunteers will be necessary for sequence development, and later for testing the robustness and repeatability of the UTE sequences. We estimate that approximately 35 healthy volunteers will be needed for sequence development and implementation.

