MIDAS: MASSIVE IRON DEPOSIT ASSESSMENT

Pearson's correlation between the HIC measured with 1.5T R2*-UTE technique and the HIC quantified by liver biopsy will be calculated and its 95% confidence interval (CI) will also be reported. If the correlation is sufficiently high, i.e., the lower bound of the 95% CI exceeds 0.7, a simple linear regression model will be established for the HIC prediction. The 95% prediction bounds will be established. If more complicated pattern shown graphically, appropriate model will be developed to describe the relationship.

Anticipated Study Completion Date: April 2017

Timeframe for Primary Outcome Measure: There will be 2 defined intervals for this study and 1 possible: (I) 1.5 and 3T MRI's, and (II) liver biopsy.

Defined Interval:

1. Screening test with the regular R2*-GRE MRI
 - The new UTE MRI will be done at the same time as the regular R2*-GRE MRI
- OR

2. Liver biopsy

Possible Interval (if liver biopsy not done first, within 30 days):

1. If the regular R2*-GRE MRI can measure the amount of iron in the liver, no other tests will be done.
2. If the regular GRE MRI cannot measure the amount of iron in the liver because the amount of iron is extremely high, a liver biopsy will be recommended to measure the exact amount of iron in the liver.

The primary objective of this study is to compare the results of the new UTE MRI with that of a liver biopsy in research participants with extremely high amounts of iron in the liver.

Data Management: Data collection and data management for this investigation will be conducted through the SJCRH Hematology Department. Co-investigators and CRAs assigned to this protocol will be responsible for assisting the PI in assuring protocol compliance as well as reviewing, transcribing and tracking of all clinical and safety related data.

Human Subjects: MRI does not involve radiation, therefore there are no risks associated with radiation injury. Study participants may need to be sedated for the MRI exam, which may expose the patients to the risks involved with anesthetics and airway complication.

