2.3 Massive Iron Overload and Absence of an Accurate Noninvasive Quantitation Method

Massive iron hepatic deposits are a common disorder in patients with iron overload. Published data and findings from an a recent multicenter trial for iron-overloaded patients (SWiTCH ,www.clinicaltrials.gov # NCT00122980), show a high prevalence of patients with very elevated HIC values, with approximately 40% of patients having biopsy-confirmed HIC ≥ 15 mg Fe/g (Table 1).^{16;29;32;33}

Table 1: Distribution of HIC values in patients with iron overload.

Study	N	HIC (mg Fe/g)			Highest HIC (mg Fe/g)
		≥ 15	≥ 20	≥ 25	
Ferritin and liver biopsy comparison study ¹³	39		10 (26%)		67.97
SWiTCH study ³⁴	145	64 (44%)	47 (32%)	24 (17%)	61.3
Calibration of MRI R2 and R2* ¹⁵	22			7 (32%)	57.8
Thalassemia Clinical Research Network ³⁴	166	55 (33%)			43
Calibration of MRI R2 ²⁹	105			12 (12%)	42.7
Calibration of MRI ³³	26			6 (23%)	not provided
STOP study ²³	39	26 (39%)		10 (26%)	41.3

Although different groups have successfully calibrated R2 and R2*-MRI techniques with liver biopsy-proven HIC,^{11;16;29} no previously developed technique has been able to accurately quantify HIC in patients with massive iron overload because of the exceedingly fast signal decay produced by high concentrations of tissue iron, which cannot be captured with current R2-spin

echo (SE) and R2*-gradient echo (GRE) techniques. The prediction accuracy that can be achieved with an R2*-GRE iron quantification sequence – which is favored over R2-SE because of the short acquisition time of a single breath-hold – deteriorates when signal decay ($1/R2^*$) is about the echo time (TE) of the first echo and the signal of the first echo falls near the noise level.¹⁶ In other words, the error in predicting iron values for $R2^* > 500$ Hz (~15 mg Fe/g) is significant, but even higher for $R2^* > 900$ Hz (~25 mg Fe/g).³³ Also, the minimum TE of conventional MR sequences cannot be much shorter than 1 ms for technical reasons. The only method to obtain accurate estimates of iron concentration in patients with extremely high R2* values ($R2^* > 500$ Hz, HIC > 15 mg Fe/g) in a typical measurement time of a single or a few breath-holds is to shorten the minimum TE substantially, which has not been previously tried for quantifying tissue iron.

2.4 Risk of Inappropriate Monitoring of Iron-Chelation Therapy in Heavily Iron-Overloaded Patients

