On the basis of these results, R2*-GRE is now the standard of care for iron quantification of research participants at St. Jude. Since the introduction of R2*-GRE as clinical order at St. Jude in 2008, we have performed over 150 iron tests. Biopsies are performed at St. Jude only for research participants enrolled on a clinical protocol that requires liver biopsy or for those with clinical indication for liver biopsy (e.g., patients with massive iron overload, or for those whose architectural structure of the liver is needed).

Although the calibrated R2*-GRE method was successfully applied in the MRIRON study, it had shortcomings:

1. The T2* fit failed for massively overloaded research participants (liver iron content > 25 mg Fe/g) because the liver MR signal vanished before the first image of the R2*-GRE image series was acquired. The chi-square goodness-of-fit test rejected pixel values if the difference between measured and model data was more than 1% and/or the fit value for R2* was greater than 1000 Hz, either of which usually occurs for HIC values of 25 mg Fe/g or higher. Other investigators have also reported a breakdown of their fitting routines at approximately 700–1000 Hz.^{11;59} Therefore, current R2*-MRI methods can only detect *massive* iron deposit in the liver, but not quantify it accurately. Without biopsies, the clinician has to manage chelation therapy blindly until there is unloading into the "MR sensitive" range of HIC.
2. MRIRON research participants with HIC values between 15 and 25 mg Fe/g (R2* = 500–900 Hz) displayed larger deviations from the prediction curve (up to ± 6 mg Fe/g; ~30%; see Fig. 1B), which limits the accuracy of the method and can be potentially risky to patients if these numbers under- or overestimate true HIC value.

The precision of MR-based iron quantification and the range over which R2* can be precisely detected need to be increased for adequate clinical monitoring of highly iron-overloaded patients. Our preliminary studies indicate that increasing errors in R2*-GRE-based HIC quantification starting with an HIC of approximately 15 mgFe/g (R2* > 500 Hz) are driven by fundamental limits on the precision of R2* estimated by curve fitting in pixels with high R2* relaxivity (high iron content).

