Figure 2 shows the 95% confidence interval for the T2* fit derived from the precision calculations and overlaid on the Bland–Altman plot in Fig. 1B. The simulation (red curve) shows that there is a nonlinear change in precision. This change is not easily recognized in the low to moderately iron-overloaded population (<15 mg/g), and therefore may have been missed by other investigators. The simulation confirmed our experimental observation of a large imprecision for higher iron overload with the standard R2*-GRE method. Other researchers have reported higher HIC values using standard R2*-GRE, but these data points demonstrated larger errors or deviated from the linear regression line.^{16;59} Interpretations of these findings focus on the multi-exponential signal decay or nonlinear relationship between HIC and R2*-GRE, respectively, in highly overloaded areas of the liver.⁵⁹ Because the results of our fit precision simulations and experimental data are in concordance, we conclude that the fit imprecision at

higher HIC is the major source of inaccuracy between HIC and R2*-MRI while measuring iron overload in patients; other potential sources of error may be negligible.

Our simulation model gives the upper limit on the R2* fit precision obtained with a specific MR sequence (e.g., R2*-GRE). With the proposed R2*-UTE sequence, which yields optimized precision for high R2* values too, we can characterize other potential factors impacting the correlation between HIC and R2*. Although multi-exponential or nonlinear behavior cannot be ruled out by using current methods, a more accurate quantification of large R2* species can help determine the true correlation between HIC and R2*-MRI and ultimately the distribution of hepatic iron stores in patients with massive iron deposition.

[figure not shown]

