4.3 Liver biopsy

Indications for liver biopsy include, but are not limited, to the need to quantify liver tissue iron and the need to obtain histopathological information of the liver tissue. Liver biopsies will only be performed if clinically indicated. Liver biopsy procedures will be performed by an interventional radiologist at St. Jude Hospital for subjects under the age of 26. Biopsies for subjects 26 years of age and older will occur at an adult facility (Regional One Health, or other adult hospital). The technique to be used is coaxial percutaneous (transcapsular) technique; however, a coaxial transjugular technique may be performed in subjects with increased bleeding diathesis, since it is associated with less hemorrhagic risk. Subjects will undergo a pre-assessment visit with the physician performing the procedure, during which the risk of bleeding will be evaluated through coagulation tests and platelet count (Table 2) performed within 48 h of the procedure. An informed consent for the procedure will be signed by subjects 18 years or older or by the legal guardian if the subject is a minor. Risks related to the coaxial percutaneous (bleeding and sclerosis of the tract) and coaxial transjugular (bleeding, carotid artery damage, arrhythmia, air embolus, and hepatic arterial venous fistula) techniques will be discussed during the informed consent process. Subjects will be required to be fasting and will be sedated for the procedure. The coaxial percutaneous biopsy technique uses a size-appropriate needle sheath that passes through the liver capsule only once. Passes are then taken through the sheath in the interior of the liver. The coaxial transjugular technique uses a sheath in the hepatic vein and passes are taken through the sheath. After the procedure, subjects will be observed and their vital signs and hematocrit monitored. Subjects will be discharged at the end of the observation period in case there are no complications. If there are signs of hemorrhage or significant pain, the subject will be admitted and treated accordingly. At least 5 mm of liver tissue will be placed in 10% formalin and sent for a pathology review at St. Jude for histology, iron stain, fibrosis, and fat content evaluation. At least 5 mm of liver tissue will be placed in a metal-free specimen vial, which will be refrigerated and mailed to Mayo Clinic Laboratory (Rochester, MN) for quantitation of liver tissue iron.

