9.2 Statistical Analysis

For the primary objective: *To explore the association of hepatic iron content (HIC) measured with the newly developed 1.5T R2*-UTE technique and HIC quantified by liver biopsy in subjects with iron overload.*

The relationship of HIC measured with 1.5T R2*-UTE and quantified by liver biopsy in subjects with iron overload will be explored graphically. If the linear relationship exists, the Pearson's correlation between the HIC measured with 1.5T R2*-UTE technique and the HIC quantified by liver biopsy will be calculated and its 95% confidence interval (CI) will also be reported. If the correlation is sufficiently high, i.e., the lower bound of the 95% CI exceeds 0.7, a simple linear regression model will be established for the HIC prediction. The 95% prediction bounds will be established. If more complicated pattern shown graphically, appropriate model will be developed to describe the relationship.

For the secondary objectives: *To explore the relationship 1) between 1.5T R2*-UTE and 1.5T R2*-GRE measurements in healthy volunteers and in subjects with iron overload and 2) between 1.5T R2*-UTE measurements with iron studies (serum iron and transferrin saturation) in subjects with iron overload.* Analyses will be implemented similarly as the analyses planned in the primary objective to explore the relationships. Pearson's correlation will be used if there is graphical evidence of linear relationship, similarly to the Primary Objective. 95% confidence interval (CI) will also be reported. If correlation is sufficiently high, a simple linear regression model will be developed and the 95% prediction bounds will be established. If more complicated pattern shown graphically, appropriate model will be developed to describe the relationship.

Objectives 1.3.1, 1.3.2, 1.3.3, 1.3.4, and 1.3.5 were classified as exploratory since they do not directly support the future implementation of the 1.5 R2*-UTE technique, and the gathering of the information from variables within these objectives is not yet clear in the near future but may ultimately generate additional hypotheses for future investigation. The purpose of the exploratory objectives is to (1) evaluate how well the R2*-UTE and the R2*-GRE signals correlate in subjects where the R2*-GRE does not fail. The analyses will provide the evidence of whether the R2*-UTE technique can replace the R2*-GRE technique even in the lower HIC

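### Section 9.2's correlation rule has no HIC range and no error by HIC level, so meeting it does not by itself show accuracy at high iron

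*Combined protocol and SAP*

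**What the plan says.** Section 9.1 builds its test of r ≤ 0.6 against 0.8 on the MRIRON finding that the correlation between R2*-GRE "and HIC is 0.56 for patients with HIC > 15 mg Fe/g", and arrives at 41 biopsies.

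Section 9.2 plots UTE-based HIC against biopsy HIC in biopsied participants with iron overload. If the plot looks linear, it computes Pearson's r with a 95% CI. The rule is: "If the correlation is sufficiently high, i.e., the lower bound of the 95% CI exceeds 0.7", a simple linear regression with 95% prediction bounds follows. If the pattern looks more complicated, another model is promised but not named. No HIC floor, range or band is stated.

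Section 9.0 gives the aim as accurate estimation at HIC of 25 mg Fe/g or more. On who will be biopsied, it says that "it is expected that most research participants who will receive the liver biopsy will have an inconclusive result by the R2*-GRE method". The protocol summary, under the timeframe for the primary outcome, adds: "If the regular R2*-GRE MRI can measure the amount of iron in the liver, no other tests will be done". Neither statement defines the analysis set. Section 4.3 also lists as an indication "the need to obtain histopathological information of the liver tissue", and section 2.6 describes biopsy at the institution for massive overload "or for those whose architectural structure of the liver is needed".

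**The concern.** The benchmark and the rule do not refer to the same HIC range. The 0.56 comes from patients above 15 mg Fe/g. Section 2.6 says the GRE fit failed above 25, so that subset probably spans about 15–25; this is my inference, as the documents do not give its spread. The 0.7 rule applies to whatever HIC range the clinically indicated biopsies produce.

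The same r can therefore stand for a small or a large error in mg Fe/g, and the clinical use described in section 2.8 depends on that error. The only error measure planned in mg Fe/g is the prediction bounds. On the linear route they appear only after the rule is met, and a simple linear regression gives them one error SD at every HIC. Section 2.7 reports that GRE precision changes nonlinearly with HIC, and says of it: "This change is not easily recognized in the low to moderately iron-overloaded population". If UTE error also rises with HIC, constant-SD bounds are too narrow where the study most needs them.

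**Working it through.** **1. The plan's own figure.** By Fisher's z, n = [(1.645 + 0.842)/(atanh 0.8 − atanh 0.6)]² + 3 = 40.6, rounded up to 41. This agrees with section 9.1.

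**2. Observed r needed at n = 41.**
- 0.6 test (9.1): tanh(atanh 0.6 + 1.645/√38) = 0.744.
- 0.7 rule (9.2): tanh(atanh 0.7 + 1.96/√38) = 0.829.

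**3. The sponsor's data.** At n = 41, the whole-cohort GRE value r = 0.96 (section 2.6) gives a lower bound of tanh(atanh 0.96 − 1.96/√38) = 0.926 and would pass. The r = 0.56 above 15 gives 0.305 and would fail. It is the same method with errors up to ±6 mg Fe/g at 15–25 (section 2.6). Part of the drop is real loss of precision and part is the narrower range; the documents do not allow the two to be separated.

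**4. What r = 0.829 means in mg Fe/g.** Average residual SD = HIC SD × √(1 − r²), and √(1 − 0.829²) = 0.559. Section 2.3 says of published cohorts: "approximately 40% of patients having biopsy-confirmed HIC ≥ 15 mg Fe/g". I use the SWiTCH row of its Table 1: 64 at ≥15, 47 at ≥20, 24 at ≥25, highest 61.3. That is 17 in 15–20, 23 in 20–25 and 24 above 25. HIC is assumed uniform within the two lower bands.
- 15–25: variance = 25/12 + (17/40)(23/40)(5²) = 2.08 + 6.11 = 8.19, so SD = 2.86.
- All ≥15: SD = 12.96, 9.90 or 7.67, with the top band assumed uniform, triangular falling to 61.3, or truncated exponential (scale 8).

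| HIC range | HIC SD | Residual SD at r = 0.829 |
|---|---|---|
| 15–25 | 2.86 | 1.6 |
| ≥15, exponential top | 7.67 | 4.3 |
| ≥15, triangular top | 9.90 | 5.5 |
| ≥15, uniform top | 12.96 | 7.2 |

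**5. The reverse direction.** As a reference size only, the MRIRON whole-cohort residual SD is 6.8 × √(1 − 0.96²) = 1.9. Within 15–25 that gives r = √(1 − (1.9/2.86)²) = 0.75, which meets the 0.7 rule about 9% of the time. A residual SD of 4.0 over all ≥15 gives r = 0.85 (HIC SD 7.67) to 0.95 (HIC SD 12.96), which meets it 69% to over 99% of the time. The larger error passes more often because the range is wider.

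**6. Constant-SD prediction bounds.** Assume UTE error SD is 10–21% of HIC, fit one straight line of biopsy HIC on UTE HIC, and use ±1.96 residual SD (1,000,000 draws, same HIC shapes, groups defined by biopsy HIC).
- SWiTCH mix: nominal 95% bounds cover about 85–88% above 25.
- All biopsies above 25: about 95% above 25 overall, but about 72–93% above 40.

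Two limits apply to the last figure. Grouping by biopsy value brings in regression to the mean; grouping by UTE value instead gives about 86–96% above 40. At the 21% end the rule would usually be missed. With HIC uniform on 25–61.3 (mean 43.15, SD 10.48), error SD = 0.21 × √(43.15² + 10.48²) = 9.3 and r = 10.48/√(10.48² + 9.3²) = 0.75. At 10% the same arithmetic gives r = 0.92.

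**The case against.** The strongest reply is that the plan expects a narrower biopsy mix than I used. Section 9.1 obtains about 200 patients by pairing 41 biopsies with the roughly 20% of patients above 25 mg Fe/g, which implies that nearly all biopsies lie above 25. Pooled bounds would then largely describe the error above 25, and step 6 shows about 95% coverage there. This stands, and it limits the size of the problem. It does not remove the dependence of r on spread within that group, nor possible under-coverage at the top of it.

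Second, the nonlinear loss of precision in section 2.7 is a GRE result. Figure 2's caption predicts a much narrower flare for UTE, better by a factor of 2 at 20 mg Fe/g and 4 at 40. This also stands. My 10–21% error has no source in the documents and is only an illustration.

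Third, 9.2 looks at the graph first and allows another model, and 9.0 says the model will be built as it was for GRE, where a Bland-Altman plot was shown. That suggests an agreement analysis, but 9.2 does not commit to one.

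A reader might infer that low-HIC biopsies will carry the study past its rule. The documents do not support that: such biopsies are possible, but their number is not given and the plan expects few. The effect depends too heavily on assumed inputs for me to attach a figure, or to call it small. Nor does 9.2 itself say that meeting the rule proves accuracy.

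**Conclusion.** The point holds in a limited form. The 0.6 null rests on a restricted HIC range, the 0.7 rule on an unstated one, and r cannot be read as accuracy without knowing the spread. On SWiTCH-shaped HIC, just meeting the rule corresponds to a residual SD anywhere from about 1.6 to 7.2 mg Fe/g. So a pass does not by itself show accuracy at 25 mg Fe/g and above, and a miss does not by itself show inaccuracy.

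The planned bounds are a useful output. They would be too narrow at the highest HIC only if UTE error grows with HIC, and by how much is unknown. The documents give neither the HIC spread of the benchmark subset, nor the eventual biopsy mix, nor the total UTE error. They do not support a conclusion that the primary test is invalid, that 41 is wrong for the test stated in 9.1, or that UTE will prove inaccurate. This is an inexpensive improvement to the analysis plan.

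**What to change.** In section 9.2:

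1. Keep the planned correlation, the rule, the 41 biopsies and the stopping rule in 3.4. State the intended HIC range, report r with the observed HIC SD, and repeat r in biopsies above 15 mg Fe/g if any fall at or below 15.
2. Whether or not the rule is met, prespecify a Bland-Altman analysis of cross-validated UTE-predicted HIC against biopsy HIC: bias and 95% limits of agreement in mg Fe/g, with CIs. Model the residual SD as a function of HIC, or report it in bands such as ≤25 and >25. Define bands by UTE-predicted HIC or by the mean of the two methods, not by biopsy HIC. Banding by biopsy builds in regression to the mean: at r = 0.829 on the SWiTCH shapes, the average prediction above 25 would shift by about −2.4 to −4.5 mg Fe/g with no fault in UTE. If residual SD rises with HIC, use weighted regression for the prediction bounds.
3. Base any statement about accuracy at high iron on item 2, not on r.

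The cost is SAP wording and a small extra analysis. The downside is imprecision. With 15 biopsies in a band, the 95% CI for the residual SD runs from √(14/26.12) = 0.73 to √(14/5.63) = 1.58 times its value, and on the expected mix the lower band may be sparse. The repeat above 15 also has less power for 0.8 against 0.6: 76% with 37 biopsies and 72% with 33, against 80% with 41.
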